**Table 1. Schedule of Assessments.**

Visit	Duration	Includes
1. Orientation @ CINC Lab (Session 1) ASAP after phone screen [Part of Baseline Appointment]	0.5 hrs	
 
- Description of study procedures and measures
 
- Informed consent; Eligibility re-screening
 
- Strain assignment for marijuana users.
 

2. Baseline Assessment @ CINC Lab (Session 1 continued) ASAP after phone screen [Part of Baseline Appointment]	1.5 hrs	
 
- Pregnancy test, Blood Alcohol Content, Toxicology drug screen
 
- Self-report of anxiety, stress and depression (e.g., GAD-7, BAI, DASS)
 
- Rumination Induction & Dot Probe Task
 
- Questionnaires on health behavior, substance use, Psychiatric interview, and psychological measures
 
- Inflammation & cannabinoid blood draw
 
- Motor & Cognitive battery
 

3. Daily follow-up assessment for all participants 1x/day for 4 weeks (~31 days) [Between Baseline, 2-, & 4-Week Appointments]	~2 mins /day	
 
- Daily online message report on anxiety/stress management, ad libitum marijuana use (if used: amount, strain, method), and sleep; individually tailored links
 

4. 2-Week Assessment @ CINC Lab (Session 2) 2-weeks after Baseline Appointment	1hr	
 
- All Baseline measures (exception: rumination induction task removed and participant global change index added)
 
- Microbiome kit & Actigraph distributed
 

5. 4-Week Assessment @ Mobile Lab (Sessions 3 & 4) Pre (Immediately) & Post (Immediately for flower or 1 hour for edible) self-administration [4-Weeks after Baseline Appointment]	2 hrs	
 
- All Baseline measures/tasks
 
- Microbiome kit & Actigraph wearable collected
 

3. Monthly follow-up assessment for all participants 1x/month for 5 additional months [After 4-Week Appointment]	~12 mins /month	
 
- Monthly online survey; individually tailored links
 

Total time (6 months)	8 hrs	Participants paid \$335

**Marijuana Administration at Home.** Unlike other studies done in the United States to date, the proposed work will utilize a design that allows participants to choose their type of administration and *ad libitum* dosing schedule, but contains an experimental element (i.e., strain assignment). Specifically, at the end of the baseline session, participants will be given instructions to purchase assigned strain, differing by THC to CBD ratio (n=75/flower strain; n=50/edible strain): 1) a THC-based strain akin to a typically used strain with normal levels of THC and little to no CBD (+THC/-CBD), 2) a 1:1 strain with equivalent THC and CBD levels (+THC/+CBD), or 3) a CBD-enriched strain with little to no THC (-THC/+CBD) at a good clinical practice dispensary in Boulder or Denver, Colorado.

The market for flower versus edible cannabis products are similar, but differ slightly in their servings, typical doses, and labeling system (potency listed by percent with flower products rather than by mg with edibles) making it currently impossible to assign identical flower and

edible potency groups, or ratios. However, Colorado requires all strains to be tested by a state licensed lab, which allows us to have a precise measure of potency to operationalize our strain assignments. Therefore, the flower groups will be assigned either the +THC/-CBD strain (containing 18% THC and <1% CBD), a combination of THC and CBD strain (a 1:1 ratio +THC/+CBD containing 12% THC and 12% CBD), or the -THC/+CBD strain (containing <1% THC and 18% CBD). Like the flower group, the edible groups will be assigned to one of the same ratios (an all THC strain, a combination of THC to CBD strain with a 1:1 ratio, or an all CBD strain) and they will choose when and how much they would like to use this assigned edible over the next four weeks. However, the participants that choose to be in the edible group (rather than the flower group), will be assigned an edible product with 10 mg of THC, CBD, or a combination of THC and CBD per edible piece (comparable to the flower products with 6, 12, or 18% THC, CBD, or a combination of THC and CBD).

The dispensary will set aside a specific lot of each flower (to be smoked or vaporized) and edible form of the assigned strain, which will be packaged in childproof bottles and labeled as “Strain C”, “Strain D” or “Strain E”, such that participants and dispensary staff will be blind to the ratio assignment until the product is purchased (THC and CBD content will be printed on the label, as required by state law), and the research staff will remain blind to which strain was assigned until after data analysis. [name] (co-investigator) will maintain the blind during the study period. The instruction to purchase “C”, “D” or “E” will be randomized across participants such that equal numbers of male and female participants are included across the ratio conditions. The design involves the instruction that participants can use as little or as much of the marijuana as they wish over the course of the four weeks of the study, and are asked not to use any other strain during that time (but if so, to just report what was used). Therefore, a research assistant will give participants that are marijuana users, a card with directions to a local dispensary. The card will have instructions to purchase a particular strain of cannabis (e.g., “strain C”) but participants will choose the amount of cannabis that they expect to use during the study (i.e., we will not assign a specific amount for them to purchase or to use during the 4-week study period). While the potency may vary slightly by the strain assignment and the amount used may vary by each person, we expect approximately one gram of flower cannabis to cost \$12 and approximately 75mg of edible cannabis to cost \$15 (comparable across typical serving amount). However, this will depend in part on what cannabis type and how much cannabis each participant chooses to use. Study staff will not provide any directions regarding dosing and administration.

Marijuana-using subjects are prompted by email to report how much was used each day using an online reporting system (RedCap). We will also provide patients with safety information that will contain warnings regarding driving or operation of machinery, consistent with the warnings used with other over the counter and prescription drugs that may impact cognitive and motor functions (e.g., Benadryl, robitussin, benzodiazepines, narcotics, etc.). The important marijuana safety warnings will include: Do not drive, operate machinery, or perform other hazardous activities while using cannabis. It may cause dizziness, drowsiness, and impaired judgment. Do not drink alcohol while using cannabis. Alcohol will increase dizziness, drowsiness, and impaired judgment. Cannabis may increase the effects of other drugs that cause drowsiness, including antidepressants, alcohol, antihistamines, sedatives (used to treat insomnia), pain relievers, anxiety medicines, seizure medicines, and muscle relaxants. More information can be found on the National Institute of Health (NIH) DrugFacts page “What is marijuana?” (<https://www.drugabuse.gov/publications/drugfacts/marijuana>).

**Rationale for Marijuana Administration Procedure.** With respect to the naturalistic aspects of the design, it is important to note that we carefully considered alternative designs. For example, we previously conducted a study that involved a highly controlled laboratory administration of low THC and zero CBD marijuana obtained from the NIDA supplier in Mississippi. However, external validity of the study was compromised because participants informed research staff that the marijuana was of significantly poorer quality than they had ever experienced. Further, although NIDA currently supplies a greater variety of marijuana strains that include some quantity of CBD, the NIDA-supplied marijuana does not reflect the levels of THC and CBD available through Colorado dispensaries and used by Colorado residents and patients ([www.drugabuse.gov](http://www.drugabuse.gov)). Thus, those procedures simply did not, and cannot reflect the strains and administration of marijuana in our and other states. In addition, the federally sourced marijuana supplied through NIDA does not currently offer any edible marijuana products ([www.drugabuse.gov](http://www.drugabuse.gov)), although these are widely available through Colorado dispensaries and used in great numbers by Colorado residents and patients to provide relief from anxiety. Thus, we are not able to acquire marijuana edibles via NIDA-supply and administer them directly to participants via a tightly controlled randomized clinical trial. Given the dearth of data available on why so many people are turning to marijuana as a treatment for anxiety and on the effects of marijuana edibles more broadly, we developed our design that naturalistically reflects common routes and methods of administration of marijuana in patients, particularly in states with legalized marijuana.

Because the long-term goal of this work is to better understand the effect of different levels of cannabinoids in anxiety patients, as they are used real world, we decided that it was critically important to emphasize external validity in both the flower and edible forms of cannabis use. The disadvantage of our design is that we have little control over how the participants use the marijuana or how much they use. To address this limitation, both in our pilot study and in this application, we rely on blood quantitation of cannabinoids (from both flower and edible users) to determine the level of THC and CBD in each subject. Thus, regardless of how the participant uses the marijuana, we have an objective measure of the dose received for both THC and CBD for each subject, which is the sine qua non of pharmacological research. This aspect is also critical for our analytic approach, which allows for the analysis of THC and CBD blood levels as continuous measures. In this way, we also capitalize on the greater variability in blood levels expected in the design by analyzing overall levels of CBD and THC as well as by strain, which by design (in flower and edible forms) will have different THC/CBD ratios. This further allows for a direct test of whether any differences in outcomes for participants randomly assigned to the -THC/+CBD strain are due to an increase in CBD or a decrease in THC as compared to their Baseline. This strain is a critical comparison as there are data to suggest that the effects of THC differ when CBD is also in the blood.

**Power Analysis and Sample Size Requirements.** Sample size was selected to permit analysis of the primary research questions at two-tailed alpha of .05 and power level of .80. Estimates of effect size follow Cohen and were conducted in G\*Power 3. The primary analyses in **Aims 1-3** broadly is the test of the group X time interaction effects across repeated assessments of THC/CBD and anxiety, inflammatory markers, and stress reactivity. For the current data analysis plan, we will only focus on the ratios and time points that we currently have supporting preliminary data for and hypothesize to have the greatest impact on anxiety. Hence, in this data analysis plan we will focus on the 3 main time points (out of 4) for a chronic use endpoint [Baseline, 2 Week, and 4-Week Pre-administration (Sessions 1-3)] and the 3 main cannabis product so that there will be

an all THC, all CBD, and a combination of THC to CBD group [(+THC/-CBD, +THC/+CBD, and -THC/+CBD, ratios: 1:0, 1:1, and 0:1)].

[figure not shown]
[figure not shown]
To be conservative, we thus estimated an ICC of .50. Using a mixed model ANOVA design, with four groups, three assessment points, and an average ICC = .5 between assessment points, a total  $n=450$  (75 per flower group and the control, and 50 per edible group) will allow us to detect a groupXtime interaction effect as small as  $f=.09$ . In **Aim 2B**, the test of the effects of group on stress-reactivity will again involve four groups ( 3 cannabis and 1 control) but only one assessment point.. Note that our power analysis is conservative, as our actual analysis will involve more powerful tests (e.g., focused interaction contrasts as opposed to overall  $F$  tests). For **Aim 3**, the estimation of the mediational model via path analysis (Hypothesis 3; see Figures 3a and 3b below), Monte Carlo simulation strategies formed the basis of our power analysis. Given that the model in Figure 3b is the more complex of the two, we utilized the model structure with the three planned contrasts as exogenous variables in our simulations. The key test of Hypothesis 3 will involve the use of structural equation modeling techniques. Because we have almost no empirical data on which to base estimates of effect size, we conservatively utilized small to moderate effect sizes depending upon hypothesized relationships. For example, we expect small coefficients (.20) from each contrast to stress reactivity, whereas we expect a slightly larger path (.40) between the contrast comparing the -THC/+CBD strain to control and inflammation. Power analyses were conducted in Mplus and then in SAS following procedures for estimating the power of the likelihood ratio test of the significance of parameters in structural equation models. We utilized Monte Carlo simulation to generate a population covariance matrix based on the hypothesized parameters in the model. For the smallest path in the model (which requires the most power to test), assuming two-tailed alpha of .05, our estimates of power at various sample sizes appear in Table 3. To assure .80 power or better to detect small associations between all groups, we thus require data from 450 participants (75 in the control and each flower group as well as 50 in each edible group) for our mediational analyses.

*The impact of attrition.* It is anticipated that some attrition will occur. Based on our current pilot study and previous marijuana studies, we anticipate a 10-15% attrition rate between the baseline session and the final four-week follow up session, though we have not experienced and do not anticipate differential attrition by condition. Thus, to allow for attrition, we assume an approximate 85% retention rate over the course of data collection. To adjust for this attrition rate in all groups, we will recruit  $n\approx520$  participants ( $n=86$ /flower or control group as well as 58/edible group). Our approach to power analysis and accounting for attrition is also quite conservative, in that the techniques we will utilize in data analysis use state of the art recommendations for the handling of missing data in longitudinal studies.

**Statistical Analysis Plan.** Analyses will be conducted primarily on the SAS system for Windows Version 9.4 and Mplus Version 7.3, which include capabilities to test multilevel models that appropriately model both normally and non-normally distributed data as well as missing data. To test the success of random assignment across the marijuana strain groups the equivalence of the three marijuana user and control groups across all pretest measures will be assessed via  $t$ -tests on continuous items (e.g., BAI) and  $\chi^2$  tests of categorical items (e.g., race). The Bonferroni approach will be used to correct for alpha inflation (familywise alpha of .05). The distributional properties of continuous variables will be examined to determine appropriate analytic techniques or normalizing transformations prior any analyses.

**Specific Aim 1** – To compare changes in anxiety in mild to moderately anxious marijuana users exposed to 4 weeks of use of one of three different marijuana strains (+THC/-CBD vs. +THC/+CBD vs. -THC/+CBD) to a group of non-using controls matched on anxiety. *Hypothesis 1* predicts a main effect of strain such that -THC/+CBD marijuana users will have lower levels of anxiety (BAI) compared to other marijuana groups and to non-using controls. To examine the main effects of group on these outcomes, we will estimate a random coefficient regression (RCR) models in SAS Proc Mixed wherein the change in BAI scores will be regressed on marijuana user group, time, and the groupXtime interaction. *Hypothesis 1* also predicts that higher CBD levels in blood among marijuana users will be associated with lower BAI. The analysis for this hypothesis will again be a RCR model, but instead of group membership, the independent variables in these models will be level of CBD in blood, time, and the CBDxtime interaction. We will conduct additional models to explore whether there may also be main effects of THC in blood or a THCXCBD interaction effect on BAI. Secondary models will test the effects of strain and /or cannabinoid blood levels on the daily and monthly assessments of anxiety using a multi-level modeling approach. These additional analyses will appropriately control for Type I error, depending upon the number of tests run. Co-I [name] has used such models extensively in prior work.

**Specific Aim 2** - To assess inflammation and stress reactivity [biological and behavioral stress change scores during a stress induction (TSST)] in mild to moderately anxious marijuana users exposed to 4 weeks of use of one of three different marijuana strains compared to a group of non-using controls matched on anxiety. *Hypothesis 2A* predicts a main effect of strain such that -THC/+CBD marijuana users will have lower levels of circulating peripheral inflammatory markers compared to other marijuana groups and to non-using controls. To examine the main effects of group on these outcomes, we will estimate a random coefficient regression (RCR) models in SAS Proc Mixed wherein the summary values of the panel of inflammatory markers utilized in our preliminary study will be regressed on marijuana user group, time, and the groupXtime interaction. *Hypothesis 2A* also predicts that higher CBD levels in blood among marijuana users will be associated with lower levels of circulating peripheral inflammatory markers. The analysis for this hypothesis will again be a RCR model, but instead of group membership, the independent variables in these models will be level of CBD in blood, time, and the CBDxtime interaction. We will conduct additional models to explore whether there may also be main effects of THC in blood or a THCXCBD interaction effect on inflammatory markers. *Hypothesis 2B* predicts a main effect of strain on reduced stress reactivity. RCR models in SAS will again be utilized, wherein stress reactivity (pre-rumination induction–post rumination induction change scores of self-report, state anxiety, and inflammatory markers) will be regressed on marijuana user group. *Hypothesis 2B* also predicts that higher CBD levels in blood among marijuana users will be associated with even lower stress reactivity. As in the test of *Hypothesis 2A*, we use RCR wherein the independent variables in these models will be level of CBD in blood. As with Aim 1, we will conduct additional models to explore whether there may also be main effects of THC in blood or a THCXCBD interaction effect on stress reactivity, with appropriate Type 1 error corrections.

**Specific Aim 3** - To test indirect effects of marijuana use on anxiety (BAI) via inflammatory markers and stress reactivity in anxious marijuana users exposed to 4 weeks of use of one of three different marijuana strains compared to a group of non-using controls matched on anxiety. Hypothesis 3 will test mediational models that ask whether the effect of marijuana use and strain on anxiety is mediated by changes in inflammation, stress reactivity, or both. To this end, we will estimate the mediational models in Figures 3a and 3b via structural equation modeling. To test the overall effect of use of marijuana versus non use, we will estimate model 3a wherein the sole exogenous variable is marijuana users (coded as 1) versus non-users (coded as 0). The mediators will be change in inflammation from Session 1 to Session 3 and stress reactivity at Session 3. The outcome variable is change in anxiety from Session 1 to Session 3. This model will be estimated and both the fit of the model and the significance of the path coefficients will be examined. Importantly, we will compare the path coefficients from user status to inflammation versus stress reactivity to determine whether use is associated with changes in inflammation, stress reactivity, or both. Assuming that the paths from inflammation and stress reactivity to anxiety are significant, we can test whether there are indirect effects of user status on anxiety that are mediated by inflammation, stress reactivity, or both. A test for completeness of mediation is employed through a 1 degree of freedom  $\chi^2$  test where a path directly from user status to anxiety is added to the model. A nonsignificant direct path and a nonsignificant change in  $\chi^2$  suggest that user group effects on the anxiety were mediated through the theoretical mediational constructs. A secondary test of mediation will utilize bootstrap methods to test the significance of, and confidence limits around, the mediated effect. Similar mediational analyses have been widely used by Co-I [name]. The model depicted in Figure 3b will test the more focused hypothesis that the ratio of cannabinoids is critical for the biological and behavioral changes that drive anxiety. The analysis will follow identical procedures to those described to test Model 3a. Finally, it is also possible to use continuous values of THC and CBD in blood as the exogenous predictors in the model.

**Amendment update Spring 2023** - We are reaching out to participants who have completed the study and have usable data in order to collect a) updated sexual orientation and gender identity (SO/GI) demographics including sex assigned at birth, and b) the Perceived Discrimination Scale (PDS). The rationale for this change is that the PDS was added late in the study and thus not all participations had the opportunity to complete the measure, and the current SO/GI-related items are not aligned with our current approach to collecting these data, which was also finalized very late in this study's course.

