We are recruiting individuals who have indicated that they are unsure of what marijuana product to try and therefore want to try any of the ratios assigned in the study, would like to continue their typical strain use, or would like to change their strain to one of the ratios assigned in this study. We will ask that all subject inform of us of their subsequent strain purchased (assigned either strain C, D, or E), and the amount of cannabis purchased (not assigned) via an online short daily message (RedCap, provided as a CCTSI resource). Participants will then self-

administer the product as they see fit, without any instructions from study staff, for 4 weeks. Marijuana users (who according to our preliminary data, typically use marijuana with a THC potency of ~18%) will be assigned to use one of three strains with differing levels of THC and CBD. Considering the wide range of potencies, ratios, and types of cannabis products used, **we will assign one of three common flower cannabis ratios** [(THC:CBD = 1:0 (18/0%), 1:1 (12/12%), and 0:1 (0/18%)] and **one of three common edible cannabis ratios** [THC:CBD = 1:0 (10 mg), 1:1 (10/10 mg), or 0:1 (0/10 mg)]. Therefore, both flower and edible users will be identically assigned to +THC alone (1:0), a combination of +THC and +CBD (1:1), or +CBD alone (0:1), and will use their assigned product *ad libitum* (using as much or as little cannabis as they would like). Users will be advised to use their assigned cannabis product as they choose (i.e., their typical behavior), while non-users (control group) will be advised not to change their behavior and all groups will be instructed to report any change to us.

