Rumination Induction (RI) Task	Focused breathing and rumination induction exercise to experimentally examine the active occurrence of rumination thought and how it affects stress and cognitive function.,, intermixed with a visual analog scale of perceived anxiety and stress used to measure changes in intensity of negative emotional responses (0-10; Rood et al 2012, Arch & Craske 2006).	

Perceived Discrimination Scale (PDS)	A 20-item scale to measure how often people feel that others treat them badly or unfairly based race, ethnicity, gender, age, religion, physical appearance, sexual orientation, or other characteristics separated into two subscales: The Lifetime Discrimination Scale and Daily Discrimination Scale.	
Positive and Negative Affect Schedule (PANAS)	Self-rated measurement of positive and negative affect with two 10-item scales from 1 (not at all) to 5 (very much; Watson 1988).	
Profile of Mood States (POMS)	The Profile of Mood States (POMS) will be used to collect baseline information on mood as well as information on mood changes throughout the study. (Johanson & Uhlenhuth, 1980; McNair, Lorr, & Droppleman, 1971).	
4-Week (Post-Administration) Appointment		
Assessment of Marijuana Potency	At the end of the experimental session, participants will be asked to report which product they received including the ratio and potency of THC and CBD in that strain.	
Appointments/Time points	Instruments/Procedures	Time to complete
Baseline Appointment (CINC Lab)	Informed consent & study orientation; BAC test; Urine toxicology & Pregnancy test; Physiological measures; Anxiety & Stress ratings; 1 st Blood draw; Questionnaires; Cognitive & Motor Battery; Microbiome distributed; Appointment 2 scheduling; Monetary Compensation.	120 minutes
Daily Follow-Up Messages (Days 1-15)	Respond to brief questions (online) about marijuana use, sleep quality, and anxiety/stress management 1x/per day for 2 weeks.	~2 mins/day x 15 days (~30 mins total)
2-Week Appointment (CINC Lab)	BAC test; Physiological measures; Anxiety/Stress ratings; 2 nd Blood draw; Questionnaires; Cognitive & Motor Battery; Microbiome & Wearable distributed; Appointment 3 scheduling; Monetary Compensation.	60 minutes

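### The plan says research staff stay blind to strain until after data analysis, but no described procedure keeps the letter codes and their contents from them

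*Combined protocol and SAP*

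**What the plan says.** - **The claim.** Section IV, Marijuana Administration at Home, states that "the research staff will remain blind to which strain was assigned until after data analysis". One co-investigator is to maintain the blind. No procedure is given.
- **The codes.** In the same subsection, products are "labeled as “Strain C”, “Strain D” or “Strain E", and "The dispensary will set aside a specific lot of each flower (to be smoked or vaporized) and edible form of the assigned strain". Three letters are described for three ratios.
- **What participants know.** They are blind only until purchase, because "THC and CBD content will be printed on the label, as required by state law".
- **How staff meet the letter.** At the baseline visit "a research assistant will give participants that are marijuana users, a card with directions to a local dispensary". It names the letter to buy; the plan's own example is strain C. The Overview and Design part of Section IV asks participants to "inform of us of their subsequent strain purchased (assigned either strain C, D, or E") through REDCap, and the daily message in Table 1 collects the strain used.
- **How the study collects the letter's meaning.** Table 2, under the 4-Week Post-Administration appointment, says that at the end of the session "participants will be asked to report which product they received including the ratio and potency of THC and CBD in that strain".
- **Who is present.** Section XVII places two trained staff in the mobile laboratory whenever a participant is there.

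**The concern.** Staff blinding needs at least one of two things to stay hidden: which letter a participant has, or what the letter means. Here staff handle the letter, and the study itself asks participants for the meaning.

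The report comes at the end of Session 4, when the reporting participant's own in-person data are essentially complete, so for that person the leak is harmless. But a letter is shared by about a third of the cannabis users. Once its meaning is known, it is known for everyone else with that letter, including those who have yet to attend Sessions 2 to 4.

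Two things are at stake. The study team conducts the rumination induction, whose before-and-after change scores are the Hypothesis 2B outcome, and runs the cognitive and motor batteries. Knowing the ratio could affect how these are delivered. Separately, a report that repeats the blinding sentence would claim a safeguard that the procedures did not secure.

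**Working it through.** The plan gives no figure on this point, so there is none to reproduce. The check has two parts.

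**1. Is there a barrier?** Taking the passages together:
- Letter: on the card handed over by a research assistant, in the online purchase report, and in the daily message.
- Meaning: on the product label, and in the Session 4 report.
- Protection: Section XIV says data are recorded in survey software, but not that session staff or analysts are kept from these fields. No participant-specific codes, change of letters over time, masked entry or separate assessors are described.

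**2. How fast would the code be known?** Inputs:
- Three letters, equally likely: Section IV gives 75 per flower strain and 50 per edible strain.
- Planned users: 3 × 75 + 3 × 50 = 375, of whom 225 (60%) use flower and 150 (40%) edible.
- Assumptions: each letter keeps its meaning, what staff learn is pooled, and successive reports are independent.

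Two different decoded letters reveal the third. The code is therefore incomplete after *k* reports only if all *k* carry the same letter:

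P(known by *k*) = 1 − 3 × (1/3)^*k*

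| Reports | P(code fully known) |
|---|---|
| 2 | 66.7% |
| 3 | 88.9% |
| 4 | 96.3% |
| 5 | 98.8% |

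Mean number of reports: 1 + 1/(2/3) = 1 + 3/2 = 2.5.

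**Sensitivity to what the plan leaves open**
- *Separate codes for flower and edible.* Flower alone needs 2.5/0.6 = 4.2 visits on average and edible alone 2.5/0.4 = 6.25. Both are needed, so the mean must be at least 6.25. Simulation (200,000 repetitions) gives a mean of 7.3, a median of 6 and a 95th percentile of 14. As a share of users, 14/375 = 3.7%.
- *Staff see only a share p of reports, one code.* Mean visits = 2.5/p: 5 at 50%, 10 at 25%, 25 at 10%. The last is 25/375 = 6.7% of users.
- *Both together, at p = 10%.* 7.3/0.10 = 73 visits, or 73/375 = 19.5% of users.

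The 375 is the analysable target. The Overview gives 450 users, and the attrition paragraph's group sizes give 3 × 86 + 3 × 58 = 432. Either would make these shares smaller.

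**When is a later participant exposed?** Marijuana Administration at Home and the Baseline Appointment text in Section XII both place assignment at the end of baseline. Table 1 lists it under orientation, before the baseline assessment. On the first two, baseline measures precede the letter, and exposure runs from Session 2.

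**The case against.** A reader might infer that the participant tells staff the ratio face to face, so that the blind certainly fails for everyone within a few visits. The documents do not go that far.

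- Table 2 names neither the recipient nor the mode of the report. It could be typed into survey software that staff never open. This stands: what is documented is a missing safeguard, not a disclosure.
- That the letters keep one meaning, and that flower and edible share it, is inferred from the three letters and the set-aside lots. This also stands, so 2.5 reports is the fastest case and not a prediction.
- Non-user controls receive no letter, so the leak concerns cannabis users only.
- The effect on the stated aims is limited. The Aim 1 outcome, the BAI, is self-reported by participants who know the content from purchase. Hypothesis 2A rests on assayed cytokines. The 2B change scores are self-report and inflammatory measures, so staff could influence them mainly through how the induction is run. Cognitive and motor results are not outcomes in the Aim 1 to 3 analyses. It would be wrong to infer that the main anxiety comparison is undermined by this route.
- The text does not say that session staff prepare the data, decide withdrawals or read out the recall lists, so no weight is put on those roles.

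What remains is that the plan makes a definite claim, sets up both halves of the leak, and describes nothing to keep them from meeting.

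**Conclusion.** The point holds as an unprotected blind. The staff-blinding sentence describes a property that the written procedures do not deliver, and shared letters carry any leak beyond the participant who reports.

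Given a constant mapping and pooled staff knowledge, the code is known after 2.5 reports on average in the fastest case, about 7 with separate flower and edible codes, and 25 with one code and 10% of reports visible. Even with both slowing assumptions combined, about four-fifths of the 375 users would complete Session 4 after the code was known. If staff see none of these reports, or letters change meaning, the figures do not apply, but the plan provides for neither.

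The consequence is moderate: possible expectancy effects in staff-run procedures, chiefly the rumination induction, and an inaccurate blinding statement in reports.

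Blinding of analysts is a separate matter. The planned models for Aims 1 and 2 use THC and CBD blood levels as predictors, and Aim 3 allows for them. Those levels would largely reveal the ratio behind any group label, so blindness until after analysis cannot be kept by relabelling groups.

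**What to change.** Preferred change:
1. Collect the Session 4 product, ratio and potency item, the purchase report and the daily strain field on participant-completed REDCap forms that session staff cannot open. Staff who follow up missed daily messages need only completion status.
2. Give the purchase letter in a sealed or electronic card, so that the research assistant does not see it.
3. Optionally, use more than one letter per ratio, so that one report does not decode a whole group.

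If this is not practical, replace the sentence with a statement that research staff may become unblinded during the study, and record when each staff member does.

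In either case, delete the claim that blinding lasts until after data analysis as far as analysts are concerned. Also reconcile Table 1 with Sections IV and XII on whether assignment comes before or after the baseline assessment.

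The cost is REDCap access settings and a changed card, plus extra labels at the dispensary if step 3 is taken. Visits, sample size and products are unaffected.
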